2.4.4.3 Analyses of other efficacy endpoints

The analysis of other endpoints (see [Section 2.1.3.3](#)) will be descriptive with no formal testing. Summary statistics at scheduled visits using observed values will be provided by each treatment group. Graphical presentations will also be used to illustrate trends over time.

The number (%) of patients who used rescue therapy will be summarized by treatment group during the core (see [Section 2.5.4](#)) and the entire double-blind treatment periods. A KM curve will be provided for the cumulative incidence of rescue therapy during the entire double-blind treatment period. The list of patients who used rescue therapy will also be provided (see [Section 2.5.4](#)).

UACR will be log-transformed at patient level. Summary statistics of UACR in log scale will then be calculated for each treatment group at each visit and back-transformed to provide the geometric mean and its associated percent change of UACR from baseline.

Shift tables will be provided for UACR at Week 26 and Week 79 using the pre-defined categories. That is, the number (%) of patients with progression from one category at baseline to another category at Week 26 and Week 79 will be provided by treatment group respectively. The pre-defined categories are, for urine ACR, <30 mg/g creatinine [Normal], ≥ 30 to <300 mg/g creatinine [Microalbuminuria], and ≥ 300 mg/g creatinine [Macroalbuminuria].

2.4.4.4 Analysis of ABPM substudy efficacy endpoints

Analyses of ABPM substudy efficacy endpoints will be performed on the ABPM population using all assessment collected up to Week 26, including those obtained after IMP discontinuation or introduction of rescue therapy, unless otherwise specified.

For ABPM substudy, primary and secondary efficacy endpoints will be analyzed using a similar approach as in the main-study with post-baseline missing values imputed by the retrieved dropouts & washout imputation method or by the control-based copy reference imputation method according to the criterion described in [Section 2.4.4.1](#). Each of the complete dataset will be analyzed using ANCOVA model including factors for treatment (sotagliflozin 400 mg, placebo), randomization stratum of HbA1c ($\leq 8.0\%$, $> 8.0\%$) as fixed factor, and the baseline value of the specific dependent variable as a covariate. Results from each complete dataset will be combined using Rubin's formula to provide the adjusted mean for each treatment group, as well as the between-group difference and the associated 95% CI.

All ABPM substudy efficacy endpoints will also be summarized by descriptive statistics by scheduled visits (Visit 3/Randomization, Visit 7/Week 12 and Visit 9/Week 26). The descriptive statistics will include number, mean, SE, standard deviation, minimum, maximum.

Please refer to Appendix C and Appendix D for ABPM substudy efficacy variable derivation.

2.4.4.5 Multiplicity issues

To control the family-wise type I error, a fixed-sequence testing procedure will be applied.

Once the primary variable (Change from Baseline to Week 26 in HbA1c) is statistically significant at $\alpha = 0.05$ (2-sided), the following main secondary efficacy variables and ABPM substudy primary endpoint will be tested in the following prioritized order. The testing will stop as soon as an endpoint is found not to be statistically significant at $\alpha=0.05$ (2-sided).

- Change from Baseline to Week 26 in 2-hour PPG following an MM
- Change from Baseline to Week 26 in FPG
- Change from Baseline to Week 26 in body weight
- Change from Baseline to Week 12 in SBP for patients with baseline SBP ≥ 130 mmHg
- Change from Baseline to Week 12 in SBP for all patients
- Change from Baseline to Week 12 in average 24-hour SBP in patients from ABPM substudy (the primary endpoint of the ABPM substudy)
- Proportion of patients with HbA1c $< 7.0\%$ at Week 26.

No multiplicity adjustment will be made on efficacy variables other than those mentioned above.

2.4.5 Analyses of safety data

Safety endpoints are presented in [Section 2.1.4](#). The summary of safety results will be presented by treatment group. The safety data will be summarized for the 26-week core treatment period and the 79-week entire treatment period separately, unless otherwise specified.

The “observation period” defined in [Section 2.1.4](#) is applicable in all safety analyses for the classification of AEs, determination of treatment-emergent Potentially Clinically Significant Abnormality (PCSA) values and the last on-treatment value for the laboratory, vital sign and ECG.

General common rules

All safety analyses will be performed on the Safety population using the following common rules:

- Safety data in patients who do not belong to the safety population (eg, exposed but not randomized) will be listed separately.
- The baseline value (with the exception of serum creatinine and eGFR) is defined as the last available value before the first dose of double-blind IMP. For creatinine and eGFR, the baseline value is defined as the average of all values before the first dose of double-blind IMP.
- PCSA values are defined as abnormal values considered medically important by the Sponsor according to predefined criteria/thresholds based on literature review and defined by the Sponsor for clinical laboratory tests, vital signs, and ECG (Appendix E).
- PCSA criteria will determine which patients had at least 1 PCSA during the treatment-emergent AE period, taking into account all evaluations performed during the treatment-emergent AE period, including nonscheduled or repeated evaluations. The number of all such patients will be the numerator for the treatment-emergent PCSA percentage.
- The treatment-emergent PCSA denominator by group for a given parameter will be based on the number of patients assessed for that given parameter during the treatment-emergent AE period by treatment group in the safety population.
- For laboratory parameters cited in the protocol as efficacy endpoints (including HbA1c and plasma glucose, etc), PCSA summaries will not be provided. These parameters will be summarized in [Section 2.4.4](#). For serum creatinine, and eGFR, PCSA summaries will be presented in safety [Section 2.4.5](#), while descriptive summaries in efficacy [Section 2.4.4](#).
- For quantitative safety parameters based on central laboratory/reading measurements, descriptive statistics will be used to summarize results and change from Baseline values by visit and treatment group for the 79-week entire treatment period only. Summaries will include the last on-treatment value. The last on-treatment value is commonly defined as the value collected at the same day/time of the last administration of IMP for the 79-week entire treatment period. If this value is missing, this last on-treatment value will be the closest value prior to the last administration of IMP during the 79-week entire treatment period.

- The analysis of the safety variables will be essentially descriptive and no statistical testing is planned. Relative risks versus placebo and their 95% CIs may be provided, if relevant.
- Selected safety analyses will be summarized by age, gender, race, and other pertinent subgroups (see details in [Section 2.4.5.1](#) and [Section 2.4.5.2](#)).

2.4.5.1 Analyses of hypoglycemia

Analyses of hypoglycemia will be performed on the treatment-emergent AE periods as defined in [Section 2.1.4](#). Hypoglycemia will be classified as severe hypoglycemia, documented symptomatic hypoglycemia, asymptomatic hypoglycemia, probable symptomatic hypoglycemia or relative hypoglycemia [Section 2.1.4](#).

The number (%) of patients with any hypoglycemia, severe hypoglycemia, and documented symptomatic hypoglycemia will be summarized respectively by treatment group during the treatment-emergent AE period, as well as the incidence rate in patient years. Two types of incidence rates will be presented: the number of patients with at least 1 event per 100 patient-years (calculated as the number of patients with at least 1 event / total exposure in 100 patient-years), and the number of events per 100 patient-years (calculated as the total number of events / (total exposure in 100 patient-years)). Note: here exposure in days is duration of treatment-emergent AE period, ie, duration of IMP treatment in days +1 ([Section 2.1.4](#)).

The summary of frequency and incidence rate in patient years for severe hypoglycemia or documented symptomatic hypoglycemia will be provided as appropriate by gender (Male, Female), age group (<50, ≥ 50 to <65, ≥ 65 years) and race (White, Black or African American, Asian, Other).

A KM curve will also be provided by treatment group for the time to first severe hypoglycemia or documented symptomatic hypoglycemia during the treatment-emergent AE period for the 79-week entire treatment period only (see [Section 2.5.4](#)).

Documented symptomatic hypoglycemia maybe presented by ≤ 3.9 mmol/L (70 mg/dL) and < 3.0 mmol/L (54 mg/dL) respectively, as appropriate.

A listing of patients for all events reported on the dedicated eCRF “Hypoglycemic event information” page will be provided with flagged category (ie, severe hypoglycemia, documented symptomatic hypoglycemia, asymptomatic hypoglycemia, probable symptomatic hypoglycemia or relative hypoglycemia).

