11.4.3.2 Analyses of hypoglycemia

The number (%) of patients and rate in patient years (2 types: the number of patients with events or the total number of events per 100 patient-year) of all, severe, and documented symptomatic hypoglycemia will be summarized by treatment group respectively. Their pattern of occurrence over time will also be assessed, as appropriate.

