2.1.4 Safety endpoints

The safety analysis will be based on the reported adverse events (AEs), hypoglycemia, and other safety information, such as clinical laboratory data, vital signs, electrocardiogram (ECG), and physical examination, etc.

Observation period

The observation period will be divided into 4 epochs:

- The **screening** epoch is defined as the time from the signed informed consent date up to the first administration of the double-blind IMP.
- The treatment epoch is defined as the time from the first administration of double-blind IMP to the last administration of double-blind IMP. This epoch includes the 26-week double-blind core treatment period and the 53-week double-blind extension treatment period. The 26-week double-blind core treatment period is the time from the first administration of double-blind IMP to the last administration of double-blind IMP on or before Visit 9/Week 26 (or Day 182 if Visit 9/Week 26 date is missing).
- The **residual treatment** epoch is defined as the time from the last administration of double-blind IMP to the last administration of double-blind IMP + 10 days (1 day for hypoglycemia).

The treatment-emergent adverse event (TEAE) period for the 79-week double-blind entire treatment period will include both **treatment** and **residual treatment** epochs (See the TEAE period for the 26-week double-blind core treatment period in [Section 2.5.4](#)).

- The **posttreatment** epoch is defined as the period of time starting the day after the end of the treatment-emergent adverse event period up to the last protocol-planned visit or the resolution/stabilization of all serious adverse events (SAE), adverse events of special interest (AESI) and events of special interest (EOSI), whichever is later.

The on-study observation period is defined as the time from start of double-blind treatment until the end of the study (defined as the last scheduled visit for those who completed the study and the date collected on e-CRF page “Completion of End of Study/Follow-up” for those who did not complete the study).

The post-study observation period is defined as the time from the day after the end of the study until the resolution/stabilization of all SAE, AESI and EOSI if applicable.

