Patients who did not experience any event during the 79-week double-blind treatment period are considered censored observations. For time to treatment discontinuation/rescue therapy, censoring date is the date of EOT. For time to severe or documented hypoglycemia, censoring date is date of EOT+1 or date of EOS, whichever is the earliest. Date of EOS will be used if date of EOT is not available. Last contact date will be used if date of EOS is not available.

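### The patient-based hypoglycemia incidence rate counts exposure after the first event, so it is too low; the shortfall is small unless hypoglycemia is common

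*SAP*

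**What the plan says.** SAP 2.4.5.1 summarizes any, severe and documented symptomatic hypoglycemia as number (%) of patients and as two incidence rates per 100 patient-years. The patient-based rate is "calculated as the number of patients with at least 1 event / total exposure in 100 patient-years". The event-based rate is "calculated as the total number of events / (total exposure in 100 patient-years". One note fixes the denominator for both: "Note: here exposure in days is duration of treatment-emergent AE period, ie, duration of IMP treatment in days +1". This matches the hypoglycemia window in SAP 2.1.4, which runs to "the last administration of double-blind IMP + 10 days (1 day for hypoglycemia" alternative). Nothing in the section stops a patient's exposure at the first event.

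Protocol 11.4.3.2 names the same pair of rates, "2 types: the number of patients with events or the total number of events per 100 patient-year", and does not define time at risk.

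SAP 2.4.5.1 also plans a time-to-first-event display: "A KM curve will also be provided by treatment group for the time to first severe hypoglycemia or documented symptomatic hypoglycemia". It covers the 79-week period only. SAP 2.5.4 ends time at the first event and, for patients without one, states: "For time to severe or documented hypoglycemia, censoring date is date of EOT+1 or date of EOS, whichever is the earliest".

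SAP 2.4.5 requires safety summaries for the 26-week core period and the 79-week entire period separately. It plans no safety testing, although relative risks with confidence intervals may be given.

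**The concern.** A rate whose numerator counts each patient at most once describes first events. A patient is at risk of a first event only until it happens. Someone whose first event falls in week 4 and who completes 79 weeks adds a further 75 weeks to the denominator, during which nothing that happens can change the numerator. Total exposure suits the all-events rate, where repeat events count; it does not suit this one.

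At stake is the accuracy of a safety summary that the SAP labels an incidence rate. A reader will take it as the rate at which patients first become hypoglycemic, and it will be lower than that. If the arms differ in incidence, the shortfall also differs between them, so a comparison of the two rates is affected.

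**Working it through.** The documents state no hypoglycemia rate or expected incidence, so there is no figure of the plan's own to reproduce. Incidence p is varied as an assumption.

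**Step 1: without assumptions.** Let N be the patients with at least one event, E their arm's total exposure as the SAP defines it, and A the part of E up to each patient's first event (all of it for event-free patients).
- Planned rate = N/E; first-event rate = N/A.
- Planned / first-event = A/E.

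The understatement, 1 − A/E, is the share of exposure that falls after a first event. It is zero only if every counted patient stops contributing exposure at that event.

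**Step 2: size under a constant hazard (assumption), full follow-up T.**
- Planned rate = p/T; first-event rate = −ln(1−p)/T.
- Factor = p / (−ln(1−p)).

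T cancels, so the factor is the same for the 26-week and 79-week summaries at equal p. The rates below use T = 552/365.25 = 1.511 years (day 551 from the flow chart, plus 1 day), per 100 patient-years.

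| p | Planned | First-event | Factor | Understated |
|---|---|---|---|---|
| 2% | 1.32 | 1.34 | 0.990 | 1.0% |
| 5% | 3.31 | 3.39 | 0.975 | 2.5% |
| 10% | 6.62 | 6.97 | 0.949 | 5.1% |
| 20% | 13.23 | 14.77 | 0.896 | 10.4% |
| 30% | 19.85 | 23.60 | 0.841 | 15.9% |

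**Step 3: dropout.** With an assumed 15% exponential dropout by the end of T (hazard μ) and event hazard λ, A/E = [(1−e^(−(λ+μ)T))/(λ+μ)] / [(1−e^(−μT))/μ]. The factors are 0.976, 0.951, 0.899 and 0.845 for λ corresponding to 5%, 10%, 20% and 30%, almost unchanged.

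**Step 4: ratio between arms, constant hazard, equal follow-up.** Planned ratio = p1/p2; first-event ratio = ln(1−p1)/ln(1−p2).
- 4% v 2%: 2.00 planned, 2.02 first-event.
- 10% v 5%: 2.00 planned, 2.05 first-event.
- 20% v 10%: 2.00 planned, ln(0.8)/ln(0.9) = 2.12 first-event.
- 30% v 15%: 2.00 planned, 2.20 first-event.

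**Step 5: can the direction reverse?** Suppose the fraction p with events all have the first one at fraction f of follow-up. Then A/E = 1 − p(1−f).
- 10% with events at f = 0.8: 1 − 0.10 × 0.2 = 0.980.
- 5% with events at f = 0.1: 1 − 0.05 × 0.9 = 0.955.

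Here the lower-incidence arm is understated more. The first-event ratio is 2.00 × 0.955/0.980 = 1.95, so the planned 2.00 is too high. The direction between arms depends on timing; the understatement within each arm does not.

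**The case against.** The strongest reply is that this is a choice of measure. The SAP prints the formula and defines the exposure, so nothing is hidden, and patients with events per total exposure is a usable exposure-adjusted count. The protocol names the same two measures, so the documents do not conflict. This stands as far as it goes, and a change of label would remove the misreading. But the SAP calls the figure an incidence rate, and under that label the denominator is wrong.

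Second, the effect is small. Patients enter on metformin alone (Protocol 7.1 and 7.2), and the 20% and 30% rows have no documentary basis. Even at 20% v 10% of 250 per arm (50 v 25 patients), an approximate 95% interval for the ratio of 2.00 is exp(ln 2 ± 1.96 × √(1/50 + 1/25)) = 1.24 to 3.23, wide beside a shift to 2.12. This stands.

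Third, a constant hazard is not assured. Rescue may include insulin, its thresholds tighten over time, and the on-treatment window continues after rescue. If first events come late, the shortfall shrinks: 2% instead of 5.1% for 10% of patients affected at 80% of follow-up. This stands as a limit on the sizes, not on the sign.

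Fourth, other outputs help: number (%), the all-events rate, a listing of every event, and the KM curve. The cover is partial. No KM curve is planned for any hypoglycemia as a whole, for the 26-week period, or for the gender, age and race subgroups in which rates for severe or documented symptomatic events are also planned.

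**Conclusion.** The point holds at low severity. Followed as written, SAP 2.4.5.1 gives a patient-based rate that is too low whenever a counted patient stays on treatment after the first event. On a constant hazard the shortfall is at most about 2.5% if incidence is 5% or less, about 5% at 10%, and passes 10% only from about 20%. It is negligible for a rare category and matters most for a common one.

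Three stronger readings are tempting and not supported:
- That the method always shrinks the difference between arms, or hides harm from sotagliflozin. The pull toward 1 needs similar event timing and follow-up, and Step 5 shows a reversal. Nor do the documents show which arm will have more hypoglycemia.
- That the rate contradicts the KM curve. The curve shows cumulative probability over time and the rate is a count per 100 patient-years. They use different risk periods but are different quantities, and neither refutes the other.
- That a trial conclusion is at risk. Safety output is descriptive, no test uses this rate, and no hypoglycemia rate ratio is specified beyond the optional relative risks.

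**What to change.** In SAP 2.4.5.1, for the patient-based rate only, define each patient's exposure as running from first dose to the first event of the category being summarized. For patients without such an event, run it to the end of the applicable treatment-emergent period (26-week core or 79-week entire). Keep total exposure for the all-events rate. Protocol 11.4.3.2 needs no change, since it leaves time at risk undefined.

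The cost is small but more than a sentence. Hypoglycemia onset dates and times are already collected (Protocol 10.6.1), and SAP 2.5.4 already has a first-event rule. That rule, however, serves only severe or documented symptomatic events over 79 weeks. Time to first event must also be derived for any hypoglycemia and for the core period, where the end-of-treatment censoring date in SAP 2.5.4 would not serve patients who continue into the extension.

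If the denominator is kept, the minimum is to stop calling the figure an incidence rate and label it as patients with events per total exposure.

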2.4.5.2 Analyses of AEs

Generalities

The primary focus of AE reporting will be on treatment-emergent AEs. Pretreatment and posttreatment AEs will be described separately.

If an AE date/time of onset (occurrence, worsening, or becoming serious) is incomplete, an imputation algorithm will be used to classify the AE as pretreatment, treatment-emergent, or posttreatment. The algorithm for imputing date/time of onset will be conservative and will classify an AE as treatment emergent unless there is definitive information to determine it is pretreatment or posttreatment. Details on classification of AEs with missing or partial onset dates are provided in [Section 2.5.3](#).

Adverse event incidence tables will be presented by SOC, HLGT, HLT, and PT, sorted by the internationally agreed order for SOCs and alphabetic order for HLGT, HLT and PT within a SOC, the number (n) and percentage (%) of patients experiencing an adverse event. Multiple occurrences of the same event by PT in the same patient will be counted only once in the tables within a treatment phase. The denominator for computation of percentages is the safety population within each treatment group.

Sorting within tables ensures the same presentation for the set of all adverse events within the observation period (pretreatment, treatment-emergent, and posttreatment). For that purpose, the table of all treatment-emergent adverse events presented by primary SOC and PT sorted by the internationally agreed SOC order and decreasing frequency of PTs within SOCs in the sotagliflozin group will define the presentation order for all other similar tables unless otherwise specified. In case of equal frequency regarding PTs, alphabetical order will be used.

Analysis of all treatment-emergent AEs

The following treatment-emergent AE summaries will be generated during the 26-week core and the 79-week entire treatment periods respectively in the safety population.

- Overview of treatment-emergent AEs, summarizing number (%) of patients with any
 - Treatment-emergent AE
 - Serious treatment-emergent AE
 - Treatment-emergent AE leading to death
 - Treatment-emergent AE leading to permanent treatment discontinuation.
- All treatment-emergent AEs by primary SOC, showing number (%) of patients with at least 1 treatment-emergent AE, sorted by internationally agreed order of primary SOC.
- All treatment-emergent AEs by primary SOC, HLGT, HLT, and PT, showing number (%) of patients with at least 1 treatment-emergent AE sorted by the SOC internationally agreed order. The other levels (HLGT, HLT, PT) will be presented in alphabetical order.
- Number (%) of patients experiencing Treatment-emergent AEs presented by PT, sorted by decreasing incidence of PT in the sotagliflozin group.
- All treatment-emergent AEs by primary SOC and PT, showing the number (%) of patients with at least 1 treatment-emergent AE, sorted by the internationally agreed SOC order and by decreasing incidence of PTs within each SOC in the sotagliflozin group. This sorting order will be applied to all other similar tables, unless otherwise specified.

- All treatment-emergent AEs regardless of relationship and related to IMP by primary SOC, HLGT, HLT and PT, showing the number (%) of patients with at least 1 treatment-emergent AE, sorted by the internationally agreed SOC order. The other levels (HLGT, HLT, PT) will be presented in alphabetical order.
- All treatment-emergent AEs by maximal severity, presented by primary SOC and PT, showing the number (%) of patients with at least 1 treatment-emergent AE by severity (ie, mild, moderate, or severe), sorted by the sorting order defined above.
- Common treatment-emergent AEs (PTs with an incidence $\geq 2\%$ in any treatment group) by primary SOC, HLGT, HLT, and PT, sorted by internationally agreed order of SOCs. The other levels (HLGT, HLT, PT) will be presented in alphabetic order.
- Summaries of common treatment-emergent AEs (PTs with an incidence $\geq 2\%$ in any treatment group) will be provided as appropriate by primary SOC and PT and by demographic factors including gender (Male, Female), age group (<50 , ≥ 50 to <65 , ≥ 65 years of age), race (White, Black or African American, Asian, Other), baseline SBP category (<130 mmHg, ≥ 130 mmHg), and baseline eGFR category (≥ 30 to <60 mL/min/1.73 m² [Moderate decrease in GFR], ≥ 60 to <90 mL/min/1.73 m² [Mild decrease in GFR], and ≥ 90 mL/min/1.73 m² [Normal]). SOC will be sorted by internationally agreed order and the PT by decreasing incidence within each SOC in the sotagliflozin 400 mg group, as described above.
- TEAEs (PTs with an incidence $\geq 5\%$ in any treatment group) by primary SOC, HLGT, HLT, and PT, sorted by internationally agreed order of SOCs. The other levels (HLGT, HLT, PT) will be presented in alphabetic order.

Analysis of all treatment emergent SAE(s)

- All treatment-emergent SAEs by primary SOC, HLGT, HLT, and PT, showing the number (%) of patients with at least 1 serious treatment-emergent AE, sorted by the internationally agreed SOC order. The other levels (HLGT, HLT, PT) will be presented in alphabetical order.
- All treatment-emergent SAEs regardless of relationship and related to IMP, by primary SOC, HLGT, HLT, and PT, showing the number (%) of patients with at least 1 treatment-emergent SAE, sorted by the internationally agreed SOC order. The other levels (HLGT, HLT, PT) will be presented in alphabetical order.

Analysis of all treatment-emergent AE(s) leading to treatment discontinuation

- All treatment-emergent adverse events leading to treatment discontinuation, by primary SOC, HLGT, HLT, and PT, showing the number (%) of patients sorted by the internationally agreed SOC order. The other levels (HLGT, HLT, PT) will be presented in alphabetical order.

Analysis of adverse events of special interest

The summaries of AESI will be presented for the 79-week entire treatment period only in the safety population.

Pregnancy and overdose will be included in overall AE summaries if any are reported. ALT increase >3 x ULN is included in laboratory PCSA summary if any.

In addition, the number (%) of patients with an AESI will be summarized by PT and by treatment group during the 79-week entire treatment period only. Corresponding listings will be provided as appropriately.

Analysis of events of special interest

The summaries of EOSI will be presented for the 79-week entire treatment period only in the safety population.

CV events, bone fracture and DKA

For EOSIs that are adjudicated (ie, deaths, myocardial infarction, stroke, and unstable angina requiring hospitalization, heart failure requiring hospitalization, bone fracture, and diabetic ketoacidosis), the number (%) of patients with an EOSI positively adjudicated by CEC will be summarized by treatment group. All EOSIs sent for adjudication and/or reported by the investigators in the specific AE forms will be listed along with the adjudication outcome.

Renal events

For the EOSI renal events where selected events are adjudicated, the number (%) of patients with any renal events identified in [Table 3](#) in [Section 2.1.4.2](#) will be summarized by treatment group.

The following renal events will be listed along with the adjudication outcome if applicable, including events,

- i. recorded in eCRF “GFR decrease”,
- ii. recorded in eCRF “Renal Event – Dialysis”,
- iii. identified as “Renal transplant” in eCRF “Other procedure”,

Renal death will be part of all deaths specified above.

Other EOSIs

For EOSIs that are not adjudicated, the number (%) of patients with at least one event will be summarized by treatment group and by PT (as identified in [Table 3](#) in [Section 2.1.4.2](#)).

Severe hypoglycemia will be included in the summary of hypoglycemia (See [Section 2.4.5.1](#)).

AE leading to an amputation is described in the section below.

Analysis of Amputation

The number (%) of patients with amputation will be summarized by treatment group and by PT and LLT during the study (ie, regardless of on- or post-treatment). Amputation is a procedure recorded in eCRF form “Other Procedures related to Amputation”. Patients who had a procedure related to amputation will be listed.

The number (%) of patients with an “AE leading to an amputation” will be summarized by treatment group and by PT. The “AE leading to an amputation” is determined by the AE identifier recorded in eCRF “Other Procedures related to Amputation” when “AE correction” is chosen as the reason for the amputation procedure.

In addition, the number (%) of patients with an “AE potentially leading to an amputation” will be summarized by treatment group and by PT (as identified in [Table 3 in Section 2.1.4.2](#)). These PTs in [Table 3](#) were requested by the European Medicines Agency (EMA)/ Pharmacovigilance Risk Assessment Committee (PRAC) Assessment Report, 9 February 2017). The associated list will be provided as well, with patients who had an amputation procedure flagged. “AE potentially leading to an amputation” represents the condition that may potentially lead to the amputation procedure, but not in all cases an amputation has occurred.

Analysis of pretreatment and posttreatment AEs

- All pretreatment AEs by primary SOC and PT, showing the number (%) of patients with at least 1 pretreatment AE, sorted by the internationally agreed SOC order and decreasing incidence of PTs within each SOC in the sotagliflozin group
- All posttreatment AEs by primary SOC and PT, showing the number (%) of patients with at least 1 posttreatment AE, sorted by the internationally agreed SOC order and decreasing incidence of PTs within each SOC in the sotagliflozin group.

Listings

Supporting AE listings will be provided for all AEs, SAEs, death, AEs leading to treatment discontinuation and/or death, and EOSI if appropriate.

Listing of all AEs, SAEs, deaths, and AEs leading to permanent treatment discontinuation, sorted by treatment, patient ID, onset date, will include the following information: treatment, patient ID, country, age, sex, race, BMI, primary SOC, PT, reported term, onset date, study day (relative day to the start date of double-blind treatment), AE duration, duration of exposure, intensity, corrective treatment, action taken with IMP, date of treatment discontinuation (if relevant), relationship to IMP/NIMP, outcome, date of death if any, seriousness, seriousness criteria, and AE status (“E” for a TEAE; “P” for an on-study post-treatment AE).

